### 3.4 Restarts and dose adjustments due to side effects

A standardized management plan for potential side effects and symptoms is detailed in section 5.7 Safety issues. If a common, non-serious side effect to the study drug develops which is noticeable but tolerable, investigators will follow a standardized management plan as outlined in section 5.7 of the protocol. These side effects include ones commonly seen with TCAs such as constipation, dry mouth, weight gain, bloating, dizziness, insomnia. The management plan for these common, non-serious side effects generally involves patient education about the side effect and adding over the counter therapies. The study drug is continued with dose escalation. If the side effect becomes bothersome and barely tolerable, then the study drug dosage is reduced to the last dose tolerated without stopping treatment. If the side effect is intolerable, then the study drug is discontinued for one week and then restarted at the lower dosage that was previously tolerated.

If side effects occur that may be more serious, such as heart palpitations, skin rash, anxiety, confusional states, panic, then the patient will be evaluated. For heart palpitations, an ECG will be

obtained. Investigators can initially attempt dose reduction to the previous well tolerated dose instead of treatment interruption. If patients developed serious or intolerable side effects requiring cessation of study drug, the drug will be stopped for one week. If the side effects disappear, a second attempt will be made to reintroduce the study drug after one week at the previous lower dose that the participant tolerated better. If the dose is well tolerated, the patient will be continued at this dose for the remainder of the study without further dose escalation. If the study medication is stopped, the patient will no longer receive the study drug, but will be followed in the study according to the protocol, in keeping with the "intention-to treat" paradigm.

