#### **SERIOUS SIDE EFFECTS FOR WHICH STUDY MEDICATION WILL BE STOPPED AND THE PATIENT WILL BE FOLLOWED ON NO TREATMENT.**

Patients will call in if they develop blurred vision, rapid heart beat, chest pain, orthostatic hypotension, dizziness upon standing or difficulty urinating.

**Cardiovascular:** Cardiac dysrhythmias, QTc prolongation (concern is for >440 – 450 msec in men or > 460 – 470 msec in women), concern for development of Torsades de Pointes or sudden death heartblock on ECG myocardial infarction (rare). Stop study medication. Ensure immediate follow-up with a cardiologist. Patient remains in study on no treatment. Repeat ECG after stopping study medication.

**Hematologic:** Agranulocytosis (rare), bone marrow depression (rare), drug-induced eosinophilia (rare), thrombocytopenia (rare). Stop study medication. Ensure immediate follow-up with a hematologist. Patient remains in study on no treatment.

**Hepatic:** Decreased liver function (rare), jaundice (rare). Stop study medication. Ensure immediate follow-up with a hepatologist. Patient remains in study on no treatment.

**Dermatologic:** Signs of an allergic reaction – unexplained hives, unexplained swelling, wheezing, swelling of face, lips, tongue, or throat. Stop medicine. Instruct patient to call 911 or go to emergency room for immediate care. Patient remains in study on no treatment.

**Neurologic:** Cerebrovascular accident (rare), seizure (rare). Stop study medication. Ensure immediate follow-up with a neurologist. Patient remains in study on no treatment.

**Psychiatric:** Depression, worsening, suicidal thoughts, suicide - Stop medicine. Refer to mental health professionals. Patient remains in study on no treatment. Symptoms of aggressiveness, akathisia (psychomotor restlessness), agitation, anxiety, insomnia, irritability, hostility, mania, impulsivity, and panic attacks may represent precursors to emerging suicidality.

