### 5.9 Management of concomitant conditions

All other illnesses will be managed in conjunction with the patient's primary care physician according to the protocols described in the Standards of Care for Patients with Idiopathic Gastroparesis (SOP IV) document prepared by the GpCRC Steering Committee.

In the event of major dermatological reactions such as generalized urticaria, bullous rashes, exfoliative dermatitis, or Stevens-Johnson Syndrome, study medication will be discontinued immediately and not restarted. For local skin reactions, study medication may be discontinued if the skin reactions are potentially drug related. If the rashes clear, the study medication may be restarted. If local skin reactions recur with restarting the study medication, study medication should be discontinued. In cases where the study medication has been discontinued, the study medication will be unmasked after the completion of the trial and the participant, investigator, and the primary care provider will be notified in order to prevent future exposures.

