#### 5.12 Procedures for unmasking treatment assignment

Treatment assignments are double masked throughout the study until all data collection for the NORIG trial has been completed (i.e., after completion of the 18 weeks of treatment and follow-up for all patients). Every effort will be made to maintain the masking throughout the study except in emergency situations. The code for masked study drug will not be broken without the knowledge of the clinical center's principal investigator. Even if the study drug is interrupted or terminated, as needed, the participant will continue with remaining NORIG follow-up visits as scheduled.

Unmasking of study medication will occur under the following conditions:

- **Severe allergic reaction (Stevens-Johnson Syndrome):** Study medication is stopped indefinitely. The patient, primary care provider (PCP), and the investigator will be unmasked.
- **Pregnancy during the study:** Study medication will be stopped indefinitely, and the coded medication will be unmasked. The patient, PCP, and investigator will be notified of the assigned treatment and the associated risks of teratogenicity.
- **Development of significant arrhythmias:** Study medication is stopped indefinitely. The patient, primary care provider (PCP), and the investigator will be unmasked.
- **Development of persistent electrolyte imbalance:** As described in Section 5.7, if the electrolyte imbalance has not been remedied with oral supplementation as indicated by a serum potassium of <3.0 mEq/L and serum magnesium of less than 1.0 mEq/L, the study drug will be stopped. The patient, primary care provider (PCP), and the investigator will be unmasked.
- **Development of persistent enzyme elevation:** As described in Section 5.7, if alkaline phosphatase, alkaline aminotransferase (ALT), or aspartate aminotransferase (AST) enzyme elevations persist above 3 times the upper limit of normal, the study drug will be stopped. The patient, primary care provider (PCP), and the investigator will be unmasked.

- **Development of thrombocytopenia:** As described in Section 5.7, if thrombocytopenia <100,000 cells per  $\mu\text{L}$  develops, the study drug will be stopped. The patient, primary care provider (PCP), and the investigator will be unmasked.

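### Section 3.4 directs reintroduction of study drug after serious side effects that clear, with no exception for the events after which sections 5.7, 5.9 and 5.12 end treatment

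*Protocol*

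**What the plan says.** Section 3.4 sets the restart rule. For side effects that are serious or intolerable and require cessation: "If patients developed serious or intolerable side effects requiring cessation of study drug, the drug will be stopped for one week". If they disappear, "a second attempt will be made to reintroduce the study drug after one week at the previous lower dose", and a patient who tolerates that dose stays on it without further escalation. The section closes: "If the study medication is stopped, the patient will no longer receive the study drug". It opens by referring to 5.7 for the management plan.

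Section 5.7 has a separate list headed "SERIOUS SIDE EFFECTS FOR WHICH STUDY MEDICATION WILL BE STOPPED AND THE PATIENT WILL BE FOLLOWED ON NO TREATMENT". It covers cardiovascular, hematologic, hepatic, allergic, neurologic and psychiatric events. The cardiovascular entry, which includes QTc prolongation, reads: "Stop study medication. Ensure immediate follow-up with a cardiologist. Patient remains in study on no treatment". The other organ systems end the same way.

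Two further sections agree with 5.7 for named events. Section 5.9 says of major dermatological reactions that "study medication will be discontinued immediately and not restarted". Section 5.12 says of significant arrhythmias and of severe allergic reaction: "Study medication is stopped indefinitely".

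On a smaller matter, for effects that may be more serious, including palpitations and confusional states, 3.4 adds: "Investigators can initially attempt dose reduction to the previous well tolerated dose instead of treatment interruption". The entries in 5.7 for confusion, and for palpitations with a normal ECG, give only a one-week stop followed by a lower dose.

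**The concern.** Section 3.4 is the section on restarts, so it is where a site will look for the restart rule. Its rule names serious effects, is worded as a direction, and excepts nothing. Section 5.7 wants no further drug after QTc prolongation, seizure or suicidal thoughts, even if they resolve. If a QTc prolongation is gone on the repeat ECG that 5.7 orders, 3.4 directs a restart and 5.7 forbids one. At stake are re-exposure of individual patients to nortriptyline after a serious event and uniform handling across seven centers.

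**Working it through.** The protocol states no figure to reproduce. The check is a comparison of current text, followed by simple exposure arithmetic.

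**Comparison of the rules**

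| Event | Section 3.4 | Other section |
|---|---|---|
| Serious side effect on the 5.7 list that clears | Stop one week, then reintroduce at the previous lower dose | 5.7: stop, follow on no treatment |
| Major skin reaction | Same rule, no exception | 5.9: no restart |
| Significant arrhythmia, severe allergic reaction | Same rule, no exception | 5.12: stopped without limit of time |
| Intolerable common side effect | Stop one week, then lower dose | 5.7 severity table: the same |
| Confusion; palpitations with normal ECG | Dose reduction allowed first | 5.7 entries: one-week stop, then lower dose |

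The 3.4 rule matches 5.7 for intolerable common effects. The conflict comes from including serious effects in the same sentence.

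**Extra exposure after a serious event at week w**

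Inputs: 15 weeks of treatment and the dose steps in 3.3 (10 mg to week 3, 25 mg to week 6, 50 mg to week 9, then 75 mg); scheduled on-treatment ECGs at weeks 9 and 12 (5.4, Appendix 9.2); a one-week stop (3.4). The calculation assumes on-schedule escalation, clearance within the week and a tolerated restart. Taper weeks are not counted.

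- Weeks on drug under 5.7: w.
- Maximum weeks on drug under 3.4: w + (15 − (w + 1)) = 14.
- Maximum extra exposure: 14 − w. The minimum is 0, if the effect does not clear.

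| Event | Dose at event | Restart dose | Maximum extra weeks |
|---|---|---|---|
| Just after week 3 | 25 mg | 10 mg | 14 − 3 = 11 |
| Just after week 6 | 50 mg | 25 mg | 14 − 6 = 8 |
| Week 9 ECG | 50 mg | 25 mg | 14 − 9 = 5 |
| Week 12 ECG | 75 mg | 50 mg | 14 − 12 = 2 |

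Before week 3 the patient is on the 10 mg starting dose, so there is no lower dose to return to.

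**Per-protocol membership**

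Section 6.3 excludes patients with less than 60% of treatment: 0.60 × 15 = 9 weeks. Under 5.7 a patient stopped at w < 9 is excluded. Under 3.4 the same patient is included if the restart lasts at least 9 − w weeks (for w = 6, 3 weeks, with 8 available). With no lower dose before week 3, membership can differ only for 3 < w < 9.

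For confusion and normal-ECG palpitations, dose reduction gives 15 weeks on drug and the one-week stop gives 14. Both exceed 9, so no set changes.

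**The case against.** The strongest reply is that 5.7 already governs. Section 3.4 sends the reader there, as does 5.4, and a general summary is normally read subject to the specific list it cites. In addition, the examples in the 3.4 paragraph are palpitations, rash, anxiety, confusional states and panic, not infarction or seizure. Reintroduction also depends on the effect disappearing, which stroke or infarction often would not satisfy. This makes 5.7 the sensible reading, but no text says so. The examples in 3.4 are illustrative, its restart sentence says serious without limit, and some events on the 5.7 list can resolve within a week.

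Three stronger readings are tempting, and the objection rightly defeats them.

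- A reader might infer that the last sentence of 3.4 contradicts its own restart rule. It reads more naturally as termination, as distinct from a one-week interruption, and on that reading it accommodates 5.7. What it lacks is a statement of which events end treatment.
- A reader might give the palpitations and confusion mismatch equal weight. The 3.4 wording is permissive, 5.7 lists both effects as common, its severity table allows reduction without stopping for barely tolerable effects, and 5.4 allows either course. The difference is one week on drug.
- A reader might take 8 to 11 weeks as the typical excess. Those figures are ceilings for early serious events. The protocol calls several of the listed events rare and gives no frequency.

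**Conclusion.** The point holds in limited form. Section 3.4, followed literally, directs re-exposure after serious side effects that clear, while 5.7, 5.9 and 5.12 require no further drug for listed events. The pointer to 5.7 does not settle which rule prevails. For QTc prolongation found at a scheduled ECG, the excess is at most 5 weeks (week 9) or 2 weeks (week 12). A larger excess needs an earlier serious event, clearance within a week and a tolerated restart. How many patients would be affected cannot be estimated from the protocol.

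This is an internal inconsistency bearing on safety and uniform conduct. A reader might infer a threat to the primary analysis, but the intention-to-treat set is unchanged because patients are followed and analyzed as randomized whatever their course of treatment. The only analysis set that could change is the per-protocol set, for serious events between weeks 3 and 9. The palpitations and confusion mismatch is minor.

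**What to change.** - **Section 3.4:** limit the stop-and-reintroduce rule to intolerable side effects not listed as serious in 5.7, and add: *Study drug is not reintroduced after any event for which section 5.7 (serious side effects), 5.9 or 5.12 requires stopping without restart; section 5.7 governs where sections differ.* The last clause also settles confusion and normal-ECG palpitations.
- **Section 5.4:** make the same reference where it allows a one-week stop for significant side effects.
- **Section 5.7, week 12 laboratory rules:** for thrombocytopenia and persistent enzyme elevation, replace the choice between interruption and termination with a stop. Thrombocytopenia and decreased liver function are on the 5.7 serious list, and 5.12 says drug is stopped for thrombocytopenia and persistent enzyme elevation. Without this change, letting 5.7 govern would leave a conflict inside 5.7 itself.

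The cost is a few sentences by amendment, with no extra visits, data or patients.

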### 3.5 Standard treatment recommendations

During the screening period, patients will receive a standardized set of recommendations to include dietary modification, weight loss if needed, and exercise. The patient's medications are reviewed to discontinue drugs that might exacerbate the underlying dysmotility disorder. Dietary modification and use of antiemetics or pain medications as appropriate are the primary management approaches. If symptoms require further treatment during the trial, patients will be instructed to take rescue medications that they would usually take such as ondansetron or promethazine for nausea and vomiting and propoxyphene or propoxyphene with acetaminophen for abdominal pain. These recommendations have been prepared by the GpCRC Steering Committee as standard of care in the management of patients with idiopathic gastroparesis (see Standard Operating Procedures IV: Standards of Care for Patients with Idiopathic Gastroparesis). This will help ensure that the patients in both treatment groups receive standard of care treatment for gastroparesis.

---

## NORIG Trial Protocol

### 4. Patient selection

---

#### 4.2 Inclusion criteria

Patients with moderate to severe symptoms of idiopathic gastroparesis will be studied. Patients should not have diabetic or post-surgical gastroparesis or dyspeptic symptoms with normal gastric emptying. In order to qualify for inclusion in the trial, patients must satisfy the following inclusion criteria:

1. Aged 21 – 65 years old at registration
2. Documentation of delayed gastric emptying on gastric emptying scintigraphy within 2 years of registration date, defined as greater than 60% retention at 2 hours or greater than 10% retention at 4 hours
3. Symptoms of gastroparesis for at least 6 months (does not have to be contiguous) prior to registration with Gastroparesis Cardinal Symptom Index (GCSI) score of  $\geq 21$
4. Negative upper endoscopy or upper GI series within 2 years of registration date

#### 4.3 Exclusion criteria

Patients who satisfy any of the following exclusion criteria will be ineligible for randomization in the trial:

1. Normal gastric emptying confirmed with scintigraphy
2. Diabetic gastroparesis or post-surgical gastroparesis including fundoplication
3. Another active disorder which could explain symptoms in the opinion of the investigator
4. History of significant cardiac arrhythmias and/or prolonged QTc
5. History of seizures
6. Use of narcotics (including fentanyl patches) more than 3 days per week
7. Use of tricyclic antidepressants for refractory symptoms of gastroparesis within 6 weeks prior to randomization
8. Use of strongly anticholinergic medications
9. Use of calcium channel blockers
10. Use of erythromycin
11. Clear history of failed trial of nortriptyline use for gastroparetic symptoms
12. Symptoms of primary depression or suicidal ideation
13. Contraindications to nortriptyline:
  - a) hypersensitivity or allergy to any tricyclic antidepressant
  - b) concomitant therapy with a monoamine oxidase inhibitor (MAOI)
  - c) recent myocardial infarction
  - d) glaucoma
14. Pregnancy or nursing
15. Any other condition, which in the opinion of the investigator would impede compliance or hinder the completion of the study
16. Use of a G tube, J tube, or a central catheter for nutrition
17. Use of a gastric electrical stimulator
18. Failure to give informed consent

#### 4.4 Run-in period

Patients must not have used any tricyclic antidepressants for refractory symptoms of gastroparesis within 6 weeks prior to randomization. Patients must not have used a monoamine oxidase inhibitor (MAOI) for the 6 weeks prior to randomization. Patients must not have used a narcotic analgesic for abdominal pain, strongly anticholinergic drugs, calcium channel blockers, or erythromycin on a daily basis for the 6 weeks prior to randomization. These agents are not to be used during screening nor for the duration of the trial. Patients will be interviewed in a detailed fashion at screening, randomization, and at every follow-up study visit to document the absence of such use.

Patients will be allowed to continue on prescription gastroparesis medications as well as any over-the-counter medications or dietary supplements. If using a selective serotonin reuptake inhibitor (SSRI), the patient must have been on a stable dose in the 3 months prior to randomization.

---

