### 6.3 Statistical analysis

The primary analysis will be made on “intention to treat” basis, which means that all randomized patients with GCSI scores at baseline and at any time during 15 weeks of treatment will be analyzed in the treatment group to which they were assigned. Any randomized patient who does not have the requisite GCSI scores will be treated as a non-responder and compared by assigned treatment group. Primary comparisons will be of the full nortriptyline group versus the full placebo group. Secondary, sensitivity analyses on a per-protocol basis will also be carried out, excluding patients from both groups who do not complete at least 60% (9 weeks) of the 15 weeks on assigned treatment.

Since the primary outcome measure is a binary indicator of improvement in GCSI score and since the randomization is stratified by clinic, P-values will be derived from the Mantel-Haenszel  $\chi^2$  test for stratified 2x2 tables, with stratification by clinic, comparing proportions improved in the group assigned to nortriptyline compared to the group assigned to placebo. The P-values so derived will be reported in the primary paper on the results of the trial. A P-value of 0.05 will be considered statistically significant.

Given the randomized design and adequate size planned for the NORIG trial, it is unlikely that confounding of the treatment groups by covariates related to the change in GCSI score will occur. However, if confounding should occur, sensitivity analyses using logistic regression models with GCSI score improvement as the binary response and treatment group indicator and any suspected confounders as covariates will be carried out to determine the sensitivity of the primary P-value to confounding; however, the Mantel-Haenszel derived P-value will be the primary P-value reported.

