## 9.2 Data collection schedule

Assessment/Procedure	Screening Visits			Follow-up visits Weeks from randomization					
	s1	s2	rz	3	6	9	12	15	18
Consent	X	.	.	.	.	.	.	.	.
Gastric emptying scintigraphy review	X	.	.	.	.	.	.	.	.
Upper endoscopy review	X	.	.	.	.	.	.	.	.
Baseline medical history	X	.	.	.	.	.	.	.	.
PAGI-SYM questionnaire	X	.	.	X	X	X	X	X	X
GSRS questionnaire	X	.	.	X	X	X	X	X	X
SF-36 QOL questionnaire	X	.	.	.	.	X	.	X	.
Beck Depression Inventory-II	X	.	.	X	X	X	X	X	X
State Trait Anxiety Inventory	X	.	.	.	.	X	.	X	.
Brief Pain Inventory	X	.	.	.	.	X	.	X	.
PHQ-15 questionnaire	X	.	.	.	.	X	.	X	.
Electrocardiogram (ECG)	X	.	.	.	.	X	X	.	.
Physical exam	X	.	X	.	.	X	X	X	.
Satiety test with electrogastrography (EGG)	.	X	.	.	.	.	X	.	.
Study drug dispensed	.	.	X	X	X	X	X	.	.
Review of study drug adherence	.	.	.	X	X	X	X	X	X
Follow-up medical history including review of adverse events	.	.	.	X	X	X	X	X	X
Labs	.	.	.	.	.	.	.	.	.
CBC, metabolic and hepatic panel	X	.	.	.	.	.	X	.	.
TSH	X	.	.	.	.	.	.	.	.
Plasma banking	.	X	.	.	.	.	X	X	.
DNA banking	.	X	.	.	.	.	.	.	.
Pregnancy test	X	.	X	.	.	X	X	X	.

**Physical exam:** includes measurement of weight, height, waist and hip circumferences, vital signs (temperature, heart rate, blood pressure) general physical findings

**CBC:** Complete blood count: white blood cell count, red blood cell count, hemoglobin, hematocrit, platelet count

**Metabolic panel:** sodium, potassium, chloride, carbon dioxide, glucose, calcium, magnesium, blood urea nitrogen (BUN), creatinine.

**Hepatic Panel:** albumin, total protein, bilirubin, alkaline phosphatase, alkaline aminotransferase (ALT), aspartate aminotransferase (AST)

**TSH:** Thyroid Stimulating Hormone

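### The per-protocol rule in section 6.3 takes no account of drugs that section 4.4 bars for the whole trial, and rescue use and background drug changes have no named record

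*Protocol*

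**What the plan says.** **Barred drugs.** Section 4.4 (Run-in period) lists tricyclics used for gastroparesis symptoms, MAO inhibitors, narcotic analgesics for abdominal pain, strong anticholinergics, calcium channel blockers and erythromycin. It then rules: "These agents are not to be used during screening nor for the duration of the trial". Patients are interviewed at screening, at randomization and "at every follow-up study visit to document the absence of such use".

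**Permitted background drugs.** The same section states: "Patients will be allowed to continue on prescription gastroparesis medications as well as any over-the-counter medications or dietary supplements". Its only dose-stability condition concerns SSRIs, and only before entry: "the patient must have been on a stable dose in the 3 months prior to randomization".

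**Rescue.** Under section 3.5, "patients will be instructed to take rescue medications that they would usually take such as ondansetron or promethazine for nausea and vomiting", with propoxyphene products for abdominal pain. Section 5.2 caps narcotics and propoxyphene-type rescue at three days a week. No frequency is stated for antiemetics.

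**Record.** The nearest row in the data collection schedule (9.2) is "Follow-up medical history including review of adverse events", marked at every follow-up visit.

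**Analysis.** Section 6.2 defines response from the GCSI alone. Section 6.3 compares all randomized patients as assigned, and adds a per-protocol sensitivity analysis "excluding patients from both groups who do not complete at least 60% (9 weeks) of the 15 weeks on assigned treatment".

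**The concern.** A per-protocol analysis is meant to show the treatment contrast among patients who followed the protocol. Here the protocol bans drugs that could affect the symptoms being scored, has their use checked at each visit, and then gives the finding no consequence in that analysis. The clearest case is a placebo patient who starts an open-label tricyclic, the class under test. That patient has effectively crossed over, yet qualifies as per protocol after nine weeks of placebo capsules.

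Permitted drugs raise a second, lesser point. Nausea, retching and vomiting are three of the nine GCSI items, 15 of 45 points. If rescue use and changes in background drugs are not recorded in usable form, nobody can say afterwards whether they differed between arms.

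**Working it through.** **1. The per-protocol criterion.** 0.60 × 15 weeks = 9 weeks, as stated. Time on assigned treatment is the only criterion given. A barred drug taken in any week leaves membership unchanged.

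**2. What keeping such patients does to the per-protocol placebo rate.** Take the planned placebo rate of 0.30 (section 6.5). Assume that a share *r* of placebo non-responders takes a barred agent and responds because of it. The protocol gives no value for *r*.

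- Kept as responders (present rule): 0.30 + 0.70*r*
- Excluded: 0.30 / (1 − 0.70*r*)
- Affected visits not counted toward response: 0.30

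| *r* | Kept | Excluded | Visits not counted |
|---|---|---|---|
| 5% | 33.5% | 0.30/0.965 = 31.1% | 30.0% |
| 10% | 37.0% | 0.30/0.93 = 32.3% | 30.0% |

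Exclusion removes most of the distortion, but not all of it.

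**3. Can the barred list be used as it stands?** Not for narcotics.

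| Section | Rule on narcotics |
|---|---|
| 4.4 | No daily use in the six weeks before randomization; then the agents are not to be used in screening or in the trial |
| 4.3 | Excluded if used more than three days a week |
| 5.2 | Narcotics and propoxyphene-type rescue limited to three days a week |
| 3.5 | Propoxyphene products named as rescue for abdominal pain |

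Section 5.2 groups propoxyphene with narcotic pain medication. On a literal reading of 4.4, a patient who takes rescue as 3.5 instructs has used a barred drug. The sections must be reconciled before the list can define an analysis set.

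**4. Is rescue or background use recorded?** Neither the visit lists in 5.4 nor schedule 9.2 names it. But 9.2 also omits items that are certainly asked at each visit: the global relief question, the CGPI and the barred-drug interview. The missing row shows that no record is named, not that none exists.

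**5. Size for the primary comparison (illustration).** The formula in section 6.5, with 0.30 vs 0.60, two-sided α = 0.05 and 90% power, gives 55.68, rounded up to 56 per group. This matches the protocol. Solved for power:

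Power = Φ{[|π₂ − π₁|√n − 1.96√(2π̄(1 − π̄))] / √[π₁(1 − π₁) + π₂(1 − π₂)]}

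At n = 65 and 0.30 vs 0.60: (0.30 × 8.062 − 1.96 × 0.7036)/0.6708 = 1.55, so power is 93.9%. With assumed lifts from added treatment:

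| Assumption | Placebo vs nortriptyline | Power |
|---|---|---|
| 5% of non-responders converted in both arms | 33.5% vs 62.0% | 91.1% |
| 10% converted in both arms | 37.0% vs 64.0% | 87.7% |
| 10% placebo, 5% nortriptyline | 37.0% vs 62.0% | 82.1% |
| Placebo only, +5 points | 35% vs 60% | 82.2% |
| Placebo only, +10 points | 40% vs 60% | 62.8% |

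The last row needs 10/70, one in seven placebo non-responders, to convert and none on nortriptyline.

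**6. Limit on antiemetic-only conversion.** The three items hold at most 15 points. With a baseline above 30, abolishing all three cannot give a 50% fall. At the entry minimum of 21, a fall of 10.5 is needed, so at least 11 of those 15 points must go, at two consecutive visits.

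**The case against.** A reader might infer that background and rescue treatment can change freely and uncaptured, so that the trial cannot separate drug effect from added treatment. The protocol does not support that.

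- Section 4.4 speaks of continuing existing drugs, and 3.5 of rescue the patient would usually take. New starts and dose increases are not authorised; the text is silent on them.
- Non-capture is only an inference (step 4). The follow-up medical history may record medication.
- Counting every randomized patient as assigned, whatever was added, is an ordinary treatment-policy comparison. Equal use in both arms does not inflate type I error, and heavier use on placebo pulls toward no difference. Heavier use on nortriptyline could mask worsening, since 5.7 lists nausea and bloating as side effects, but the document has no data showing this.
- A sensitivity analysis for added treatment may sit in a statistical analysis plan that is not at hand, so its absence from the protocol is not itself a fault.
- The larger power losses rest on placebo-only conversion. The 30% placebo rate comes from clinicians' experience with similar patients and may already include usual rescue. The rise from 56 to 65 per group was made for mis-specified rates.
- A stability condition for SSRIs and none for gastroparesis drugs is a difference, not a contradiction. Asking for the two to match would be a clinical proposal.

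All of this stands. It does not reach the per-protocol rule, which the protocol itself fixes and which disregards drug use that the protocol itself bars and has checked.

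**Conclusion.** The point holds in a limited form. The per-protocol set in 6.3 retains patients who took agents barred by 4.4, so it does not fully reflect protocol-adherent treatment. If 5% to 10% of placebo non-responders converted on a barred agent, the per-protocol placebo rate would rise by 3.5 to 7 points under the present rule, against 1.1 to 2.3 points if they were excluded. Those shares are assumptions.

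In addition, antiemetic rescue has no stated frequency limit, and neither rescue use nor background drug changes are named as items to record. That calls for clarification; it does not show that data are lost. The effect on primary power, about 91% to 63% at 65 per group, is illustrative and depends wholly on the assumed conversion. No figure in the protocol is wrong, and the intention-to-treat primary analysis needs no change.

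**What to change.** 1. **Reconcile the narcotic rules** in 4.4 with those in 3.5, 4.3 and 5.2. Which rule applies is for the sponsor.
2. **Extend the per-protocol exclusion in 6.3** to documented use, through week 15, of agents barred in 4.4 as reconciled. The interview that 4.4 already requires should supply the data.
3. **Name two items in the existing visit medical history**: days of rescue use, and any start or dose change of a background gastroparesis drug. Report both by arm.
4. **Keep the intention-to-treat primary analysis** and add one supportive sensitivity analysis. In it, a visit does not count toward response if, since the previous visit, a gastroparesis drug was started or increased or a barred agent was used.

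The cost is a slightly smaller per-protocol set, a few more interview questions and one extra analysis. Excluding patients for post-randomization drug use is selective, as the nine-week rule already is, so the per-protocol result should stay secondary.
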